## 2. STUDY OBJECTIVES

### **Primary objective 1**

**To describe current practice in one healthcare organisation of mobilising ICU patients receiving vasoactive drugs.**

#### Secondary objectives

1. To measure the mobilisation that occurs while patients receive vasoactive drugs in terms of the type of mobilisation and type and dosage of vasoactive drugs.
2. To describe which patients receiving vasoactive drugs are not mobilised and the reasons why.
3. To measure the adverse event rate occurring in patients mobilised on vasoactive drugs.
4. To describe how clinicians judged the risk of mobilising patients receiving vasoactive drugs.
5. To measure what standard care is in relation to mobilisation treatment milestones.
6. To measure cost of care related to ICU and hospital length of stay and mobilisation received.

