### 5.1 PARTICIPANT RECRUITMENT DATA

ICU patients will be recruited as set out elsewhere in this protocol and data about recruitment will be collected:

- Standard recruitment data that records the numbers of individuals at the different stages of the study (for example numbers eligible, numbers excluded) and any reason for not taking part at each stage. This will also include details about any consultee advice given.
- Data to inform which research staff will be required for future recruitment of patients in the RCT will be collected by measuring the number of participants recruited by the clinicians (physiotherapists, doctors or nurses), research nurses or clinician researchers.
- Whether the participant was enrolled before the first mobilisation session has occurred to measure whether this is feasible and the day of ICU stay that consent was obtained.

For each participant enrolled, the following procedures will be carried out (figure 1). In addition, for important feasibility outcomes, we have specified feasibility 'success' criteria which are an indication to consider future investigation of the mobilisation of patients receiving vasoactive drugs. If these criteria are not met, then further consideration is required before deciding whether future investigation of mobilisation of this patient group is needed.

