  - On these days, any documented reasons for not mobilising.

The following outcomes will be used to describe standard care, for potential use as surrogate outcomes in a future pilot trial or feasibility study:

- Time to first mobilisation treatment and whether this first mobilisation treatment occurred whilst the patient was still receiving vasoactive drugs.
- Time to first being able to sit out of bed, stand and walk (regardless of the assistance required) (Nickels et al., 2017, TEAM Study Investigators et al., 2015).
- ICU Mobility Scale (IMS) level at ICU discharge.
- ICU and hospital length of stay.

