## 8. STATISTICS AND DATA ANALYSIS

For the quantitative data, descriptive statistics will be used to describe and summarise the outcomes set out above. For example the mean and standard deviation or median and interquartile range for continuous variables and numbers and percentages for categorical variables. All qualitative data will be analysed using qualitative content analysis (Elo and Kyngas, 2008).

Where relevant, secondary analysis may be carried out, using descriptive statistics to describe relevant outcomes in different patient subgroups, for example those subgroups defined in a recent Delphi process carried out by the authors (IRAS project ID: 212066; REC reference: 17/LO/0830).

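### Times to first mobilisation, sitting out, standing and walking have no time origin, end of observation or rule for patients who die or leave first; if only achievers are summarised, standard care looks faster than it is

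*Combined protocol and SAP*

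**What the plan says.** One secondary objective under primary objective 1 (Section 2) is "To measure what standard care is in relation to mobilisation treatment milestones". Section 5.5 supplies the outcomes for it: "Time to first mobilisation treatment and whether this first mobilisation treatment occurred whilst the patient was still receiving vasoactive drugs", and "Time to first being able to sit out of bed, stand and walk (regardless of the assistance required". It introduces them with this purpose: "The following outcomes will be used to describe standard care, for potential use as surrogate outcomes in a future pilot trial or feasibility study".

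Section 8 is the whole statistical section. It says that "descriptive statistics will be used to describe and summarise the outcomes set out above", and then: "For example the mean and standard deviation or median and interquartile range for continuous variables". It does not mention censoring, competing events or any time-to-event summary.

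Nearby provisions do not fill the gap:

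- The rule on deceased participants in Section 5.6 concerns completion of the day-60 candidate outcomes only.
- Section 5.5 counts patients mobilised while on vasoactive drugs, and days without mobilisation with any documented reasons. It specifies no count of patients who never sat out, stood or walked.
- Section 5.1 records "Whether the participant was enrolled before the first mobilisation session has occurred", so some first mobilisations may precede enrolment.

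**The concern.** A time to a first event exists only for patients who have the event. Here some will not. Section 4.3.1 excludes only patients expected to die imminently, Section 4.2.1 asks only for an expected further ICU stay of at least 24 hours, and Section 5.6 itself foresees deaths before follow-up. A patient who dies, or leaves before standing or walking, has no value to put into a mean or a median. If nothing more is said, the summary is taken over achievers.

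The reader of the results would take that figure as the usual time to walking under standard care. It is really the usual time among those who walked, and it says nothing about how many did not. A later pilot or feasibility study that took up these times as surrogate outcomes would inherit too short a time for its usual-care group and no figure for the share who never reach the milestone.

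The missing time origin adds a separate ambiguity. Times counted from ICU admission, from the start of vasoactive drugs and from enrolment are different quantities, and the plan does not choose between them.

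**Working it through.** **Inputs.** The plan states no milestone time, milestone rate or mortality, so there is no figure of its own to reproduce. From the documents: the outcomes (Section 5.5), the example summaries (Section 8) and a maximum of 40 patients (Section 6.1). Assumed: the share *s* who never reach the milestone, taken from 10% to 40%; and, for the day figures only, constant hazards.

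**Step 1: direction, for any distribution.** Let F be the distribution of times among achievers. The proportion of all patients who have reached the milestone by day t is (1 − s) × F(t). Half of all patients have reached it when (1 − s) × F(t) = 0.5, that is, at the achievers' quantile 0.5 / (1 − s). The achievers-only median is their 0.5 quantile, which is earlier whenever s > 0.

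| s | 0.5 / (1 − s) | Achievers if 40 are enrolled |
|---|---|---|
| 10% | 0.5 / 0.9 = 0.556 | 36 |
| 20% | 0.5 / 0.8 = 0.625 | 32 |
| 30% | 0.5 / 0.7 = 0.714 | 28 |
| 40% | 0.5 / 0.6 = 0.833 | 24 |

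With 40 enrolled, half of all patients means 20. At s = 20% the 20th patient to reach the milestone is the 20th of 32 achievers (20 / 32 = 62.5%), while the achievers-only median sits between the 16th and 17th. At s = 40% it is the 20th of 24 (83.3%), against a median between the 12th and 13th. Above 50%, no all-patient median exists, yet an achievers-only median can still be printed.

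**Step 2: illustration in days.** Take a milestone hazard a and a hazard of death or departure b, with s = b / (a + b), so a + b = a / (1 − s). Then:

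- achievers-only median = ln 2 / (a + b);
- day by which half of all patients have reached the milestone = −ln(1 − 0.5 / (1 − s)) / (a + b).

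With a = ln 2 / 7 (a 7-day median if nobody died or left first):

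| s | Achievers-only median | Half of all patients | Shortfall |
|---|---|---|---|
| 10% | 6.3 days | 7.4 days | 15% |
| 20% | 5.6 days | 7.9 days | 29% |
| 30% | 4.9 days | 8.9 days | 45% |
| 40% | 4.2 days | 10.9 days | 61% |

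The sum a + b cancels in the ratio of the two medians, so under constant hazards the percentage shortfall does not depend on the time scale. A hazard of 0.05 per day gives other days (11.1 against 15.7 at 20%; 8.3 against 21.5 at 40%) but the same percentages. The days themselves carry no information about this study.

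**Step 3: small-sample check.** Simulating 40 patients 20,000 times on the 7-day scale gives typical medians of 5.6 against 8.0 days at 20%, 4.9 against 8.9 at 30%, and 4.2 against 10.9 at 40%. The all-patient median was not reached in 0.7% of runs at 30% and in 12.8% at 40%.

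**The case against.** **The plan does not say that non-reachers are dropped.** This is the strongest reply, and it stands as far as it goes. A reader might infer that the plan commits itself to a biased summary. It does not: Section 8 gives its summaries as examples, and ranking non-reachers last in a median would be compatible with the text. What the plan has is an unfilled gap whose default outcome is an achievers-only figure.

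**Survival to enrolment.** A reader might also infer that having to survive to enrolment makes care look faster still. The documents do not support that. Being still in ICU, on vasoactive drugs and expected to stay 24 hours more under-samples patients who leave quickly. For those enrolled before first mobilisation, the guaranteed waiting time lengthens times counted from admission. Both push towards slower, and the net direction is not established.

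**Delayed entry.** Modelling entry at enrolment may look like the answer, but it would drop from the first-mobilisation analysis every patient mobilised before enrolment, and would leave very small early risk sets with at most 40 patients.

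**Length of stay.** It may seem to share the defect. It does not: it has a value for patients who die as well as for survivors.

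**Consequence.** The future sample size is to be informed by the day-60 outcomes (Sections 2 and 5.6), not by milestone times, and use as surrogates is only potential. Section 5.5 also records non-mobilisation in part, and the ICU Mobility Scale level at ICU discharge. These limit the importance of the point but do not supply the missing rule.

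**Conclusion.** The concern holds in conditional form. No section gives a time origin, an end of observation or a rule for patients who die or leave before a milestone, and if only achievers are summarised, standard care looks faster than it is. The direction needs no distributional assumption. The size depends on the share who never reach the milestone, which the documents do not give: over an assumed 20% to 40%, the figure wanted lies at the achievers' 62.5th to 83rd percentile, or, under constant hazards, the reported median is 29% to 61% too short. With no non-reachers there is no bias.

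What is affected is one secondary descriptive objective and a set of possible surrogate outcomes. The key outcomes in Section 5.3, hypothetical recruitment rate and day-60 follow-up rate, are untouched. The change is worth making because it is cheap and because these times are offered for later use.

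**What to change.** Add to Section 8, for the four times in Section 5.5:

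1. One time origin, for example ICU admission, and one end of observation that matches where milestones are recorded. No section says they are tracked on the ward, so this should be ICU discharge unless ward recording is confirmed, in which case hospital discharge.
2. The number and percentage of all enrolled patients who reach each milestone.
3. In place of the mean or median, the cumulative incidence (Aalen-Johansen), with death, and discharge without the milestone, as competing events. The simpler alternative is a median over all enrolled patients with non-reachers ranked last, stated as not reached where fewer than half get there.
4. Time to first mobilisation shown separately for patients enrolled before and after their first mobilisation, using the item already collected under Section 5.1.

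The cost is a few lines of text and slightly more analysis. Milestone times, length of stay, date of death and day of consent are already planned; only ward recording, if chosen, might add work. With at most 40 patients, some medians may not be reached; where that happens, the percentage reaching the milestone is the result to report.

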## 5.6 ASSESSMENT OF DAY 60 OUTCOMES

To inform the future choice of suitable primary outcome measure for the future RCT, we will describe the feasibility of measuring candidate primary outcome measures at day 60 post-enrolment in the study. Data from outcome measurement will also inform a future sample size

calculation. The following outcomes will be recorded as soon as possible after day 60 post-enrolment.

- Mortality:

Alive/deceased status will be recorded including date of death. This will be confirmed using clinical data contained within the NHS Trust systems, from NHS Spine (a national database held by NHS Digital, but accessible within the research sites to research nurses), or contacting the participant's GP to clarify any uncertainty. The GP will be informed that the participant has been enrolled in the study after consent is taken and will be sent a copy of the participant information sheet. If no date of death is recorded, the participant will be contacted to measure the other outcome measures below. If at this point it is discovered that the participant is no longer alive, then date of death will be recorded as informed by relatives/carers.

- Health-related quality of life:

Measured using the EQ - 5D (5 Level) questionnaire (EQ-5D-5L) (EuroQol, 1990, Herdman et al., 2011, Janssen et al., 2013).

- Disability:

Measured using the World Health Organisation's Disability Assessment Schedule 2.0 (WHODAS 2.0) 36-item or 12-item version (Hodgson et al., 2017, Ustun et al., 2010).

- Physical functioning:

Because they have been shown to measure different components of physical functioning (Denehy et al., 2014), this domain will be measured using a patient-reported outcome measure (for example the physical function domain of the 36-item Short Form Health Survey Version 2 (SF-36 v2) (Ware, 2000, McDowell et al., 2017) or the physical function domain of the RAND 36-Item Health Survey 1.0 Questionnaire (RAND SF-36 v1) (Ware and Sherbourne, 1992, Needham et al., 2017)) and a performance-based outcome (6-Minute Walk Test (6MWT) (Laboratories, 2002, Needham et al., 2017)).

Firstly, the above procedures will be carried out to ascertain the participant's alive/deceased status as close to day 60 post-enrolment as possible. If no evidence of date of death is found, then the participant will be contacted to arrange a suitable time to carry out the rest of the outcomes.

Patient-reported outcome measures (questionnaires) will either be carried out over the phone, by post, or in person (e.g. if the participant is still an in-patient at the hospital site). The performance-based outcome will be carried out at the site and reasonable travel expenses reimbursed for participants as appropriate. Outcomes will be recorded as soon after day 60 as possible, with exact time to follow-up being recorded to inform the feasibility of doing so.

Feasibility of outcome measurement will be primarily assessed by the follow-up rate. Other measures of feasibility will include: number of patients where all outcomes are completed plus any reasons why outcomes were not completed, for instance drop out/withdrawal rate, loss to follow up or death. If a participant is deceased at the time of follow-up, then they will still be counted as having completed the other candidate primary outcome measures. The number of patients who completed each individual outcome will also be measured. Measures of central tendency and variability of data for each outcome will inform suitability for future primary outcome measurement and a future sample size calculation for the RCT. Feasibility success for follow-up rate will be 80% minimum (Hodgson et al., 2016). After the 31st May 2019, we will not contact patient participants directly at day 60 follow-up, for example to confirm survival status or to carry out the follow-up questionnaires or walking test. However, in order to maximise participant follow up, we will still confirm survival status by the means set out above that do not involve direct contact with the participant. We will send a letter to patients that we will not follow up in person at day 60, to inform them of the change in study procedures. If retrospective consent has not yet been gained, the letter will be sent to the consultee.

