## 5.3 KEY OUTCOMES

Key outcomes for this exploratory study are:

- Hypothetical recruitment rate for the future RCT.
- Follow-up rate of participants for day-60 outcomes.

More details about these outcomes, plus the secondary outcomes for this study are detailed below.

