## 5.7 END OF STUDY

The end of the study will be the completion of 60-day follow up for all recruited participants, or when the end date of the study is reached, whichever occurs first.

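### Deaths are credited as completed questionnaires and walk tests, and the plan does not say how they, or participants past the contact cut-off, enter the 80% follow-up criterion

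*Combined protocol and SAP*

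**What the plan says.** One of the two key outcomes in section 5.3 is the "Follow-up rate of participants for day-60 outcomes". Section 5.6 makes this rate the main measure of whether outcomes can be collected and sets a criterion: "Feasibility success for follow-up rate will be 80% minimum". No section defines its numerator or denominator, and section 8 adds only that descriptive statistics will be used.

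After the follow-up rate, section 5.6 turns to further feasibility measures, starting with the "number of patients where all outcomes are completed" and the reasons for non-completion, death among them. The rule for deaths comes next: "they will still be counted as having completed the other candidate primary outcome measures". The sentence after it reads: "The number of patients who completed each individual outcome will also be measured".

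The same section sets a cut-off. After 31 May 2019, "we will not contact patient participants directly at day 60 follow-up", but "in order to maximise participant follow up, we will still confirm survival status by the means set out above", where those means involve no direct contact. Section 9.2.3 ends recruitment on the same date, and section 9.2.5 expects some participants to reach day 60 after it. Neither section 5.6 nor the consent sections say how those participants are counted.

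**The concern.** Section 5.6 exists to show which candidate primary outcomes can be collected in this population, so that one can be chosen for the future RCT. A participant who has died supplies no questionnaire score and no walking distance. The plan assigns no score for death, so this is not a composite outcome in which death takes a value. It is a completion credit with no datum behind it. A measure that few enrolled participants can provide will look more feasible the more of them die.

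Two gaps add to this. The text does not say whether the credit also enters the per-outcome counts or the follow-up rate with its 80% criterion. It also does not say whether participants past the contact cut-off stay in the denominator. Both choices could be made after the data are seen, and either can move the result across 80%.

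The plan treats another obstacle differently. Under section 9.2.3, participants who have not regained capacity at day 60 do not do the measures, the reason is recorded, and they are kept in the study so that the feasibility result is not biased.

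**Working it through.** There is no derived figure to reproduce. The 80% is a chosen threshold and 40 (section 6.1) is a pragmatic maximum; 80% of 40 is 32. The documents give no mortality, completion or accrual figures, so those below are assumptions shown over ranges. Enrolled participants are taken as the denominator. Section 5.7 points that way, since it refers to "completion of 60-day follow up for all recruited participants", but it defines the end of the study and not the rate.

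**1. Effect of the rule on the all-outcomes count.** Let m be day-60 mortality and c the completion rate among survivors.

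- Reported rate = m + (1 − m)c
- Share of enrolled with observed values = (1 − m)c

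For example, m = 0.30 and c = 0.75 give 0.30 + 0.70 × 0.75 = 82.5% reported and 0.70 × 0.75 = 52.5% observed.

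| m | c = 50%: reported / observed | c = 75%: reported / observed | c = 90%: reported / observed |
|---|---|---|---|
| 10% | 55% / 45% | 77.5% / 67.5% | 91% / 81% |
| 20% | 60% / 40% | 80% / 60% | 92% / 72% |
| 30% | 65% / 35% | 82.5% / 52.5% | 93% / 63% |
| 40% | 70% / 30% | 85% / 45% | 94% / 54% |

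In every column the two figures move in opposite directions as mortality rises.

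**2. If the rule also feeds the 80% criterion** (cut-off ignored). Survivor completion needed = (0.80 − m)/(1 − m). With n = 40:

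| m | Survivors | Needed under the rule | Needed if 80% of survivors is required | Gap |
|---|---|---|---|---|
| 10% | 36 | 28 (78%) | 29 | 1 |
| 20% | 32 | 24 (75%) | 26 | 2 |
| 30% | 28 | 20 (71%) | 23 | 3 |
| 40% | 24 | 16 (67%) | 20 | 4 |

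At 30% mortality the criterion is met with 20 of 40 enrolled participants measured.

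**3. The contact cut-off.** 1 April 2019 + 60 days = 31 May 2019, so anyone enrolled from 2 April reaches day 60 after direct contact ends. From 1 November 2018 to 31 May 2019 is 212 days, of which the last 60 fall in this window: 60/212 = 28.3%, and 28.3% × 40 = 11.3, about 11. If enrolment starts on 1 December the number is about 13; on 1 January, about 16. If the maximum is reached early, it could be few or none.

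Let L be the number past the cut-off. If they stay in the denominator, each participant must be measured or deceased to count, and none of the L dies, the ceiling is (40 − L)/40. The last column is the number of the L who would have to die for 32 to be reached, with everyone else counted.

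| L | Ceiling | Deaths needed among the L |
|---|---|---|
| 5 | 35/40 = 87.5% | 0 |
| 8 | 32/40 = 80% | 0 |
| 9 | 31/40 = 77.5% | 1 |
| 11 | 29/40 = 72.5% | 3 |
| 16 | 24/40 = 60% | 8 |

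With L = 11 the other readings differ sharply. If the 11 are excluded, 0.8 × 29 = 23.2, so 24/29 passes. If known vital status counts as follow-up, 40/40 is possible.

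**4. Same data, different counting rules.** Assume n = 40, L = 11, m = 30% throughout, and 70% completion among contactable survivors. Expected counts: deaths 8.7 among the 29 and 3.3 among the 11; measured 0.7 × 20.3 = 14.21.

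| Rule | Calculation | Rate |
|---|---|---|
| Measured / all enrolled | 14.21/40 | 36% |
| Measured / all survivors | 14.21/28 | 51% |
| Deaths credited, late survivors missing | (14.21 + 12)/40 | 66% |
| Measured / contactable survivors | 14.21/20.3 | 70% |
| Deaths credited, late participants excluded | (14.21 + 8.7)/29 | 79% |
| Deaths credited, vital status counts for late participants | (14.21 + 8.7 + 11)/40 | 85% |

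**The case against.** The rule is disclosed in advance and deliberate. Treating death as a known end state, and not as a failure of follow-up, is a reasonable convention if the rate means that outcome status is known. Listing death as a reason for non-completion and then saying how it is counted is not in itself contradictory. That stands, but it defends a different quantity. Known status says nothing about whether a questionnaire or walk test can be obtained, which is what section 5.6 sets out to learn.

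By its position, the rule attaches to the all-outcomes count, which has no success threshold, so its link to the 80% criterion is uncertain. This also stands: step 2 applies only if the link exists, and its gap of 1 to 4 participants is small beside the exact 95% interval of 64% to 91% for 32/40.

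Little information is lost. Date of death, reasons for non-completion and completers of each outcome are all collected, so every rate can be derived later. The text leaves open, however, whether the deceased also count as completers in the per-outcome numbers.

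On the cut-off, mortality is itself a candidate outcome, and confirming survival status to maximise follow-up suggests that vital status may count. On that reading there is no ceiling problem. Section 9.2.3 also expects adequate recruitment before 31 May 2019, so late participants may be few; with 8 or fewer, 80% stays attainable. These points limit the size of the problem but do not supply the missing definition.

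Finally, under section 5.1 a missed criterion only prompts further consideration. That is why the point is not more serious.

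**Conclusion.** The concern holds and should be fixed. The rule for deaths is explicit, and following it makes the all-outcomes completion figure rise with mortality while actual measurements fall, against the purpose of section 5.6. That conclusion rests on the text and needs no assumed figures.

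The sizes are conditional. At 75% survivor completion, the reported figure exceeds the observed share by 10 to 40 percentage points as mortality goes from 10% to 40%; the difference always equals the mortality, so it is small if few die. The effect on the 80% criterion depends on whether the rule applies there. The cut-off effect depends on accrual: about 11 of 40 under even accrual from 1 November 2018, with 8 as the break-even. The missing numerator and denominator and the silence on late participants are mainly matters of clarification, but they concern a key outcome and can decide by themselves whether 80% is met.

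**What to change.** In section 5.6:

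- Remove the credit for deaths. Report completion of each questionnaire and of the walk test among participants alive at day 60, keeping those who lost capacity in the denominator as not completed.
- Show deaths as a separate category, and give the number with an observed value out of all enrolled.
- State the numerator and denominator to which the single 80% criterion applies.
- State whether participants whose day 60 falls after 31 May 2019 are included, or reported separately as not contactable by design.
- If wanted, keep a separately labelled secondary rate for outcome status known, deaths included.

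The cost is some wording and one or two table rows, with no new data. The rate will be less favourable and less precise: for example 20/28 (exact 95% CI 51% to 87%) in place of 32/40 (64% to 91%). A rate among survivors has its own selection limits, which is why the count out of all enrolled should stand beside it.
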